Study Protocol with SAP

Title:

Evaluating the Safety and Efficacy of Fractionated Carbon Dioxide Therapy in Postoperative Lower Extremity Wound Healing

NCT number:

NCT03644849

Document date:

April 7, 2021

Upload date:

November 7, 2021

Purpose: This study will evaluate the efficacy and safety of laser therapy on postoperative lower extremity wound healing over 12 weeks. We will include adult patients who have undergone Mohs Micrographic Surgery on their lower extremities. Patients with poor immune systems, current pregnancies, uncontrolled diabetes, lower extremity venous or arterial disease will not be included in this study. After surgery patients will be randomized into two groups. One group will receive a single laser treatment immediately after their surgery on their wound while the other will not. The group not receiving laser therapy will undergo a sham laser therapy treatment. Immediately after therapy and 4, 8, and 12 weeks postoperative patients will have a follow up visit. During these visits patients wound size will be recorded, whether the wound has healed, a photograph will be taken, and the wound temperature will be measured. Patient will be given a diary to record any adverse events related to the wound and will fill out a quality of life survey.

Objectives (specific aims and hypotheses): We hypothesize that the AFL carbon dioxide ablative laser is a safe and efficacious treatment for lower extremity wounds that result from skin cancer surgery. We plan to test this hypothesis in 2 specific aims:

Aim 1. We will establish the safety and tolerability of the carbon dioxide AFL for postoperative lower extremity wounds. Patients with postoperative lower extremity wounds will be randomized to sham laser versus laser therapy. At designated time points 0-12 weeks after sham or laser treatment, patients will return to clinic for assessment of safety endpoints, including the incidence of wound infection and tolerability using a patient diary and health-related quality of life measured using a standardized generic questionnaire such as EQ. A sample size of 48 is appropriate.

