Patients will be seen at 4 separate visits to monitor safety and efficacy endpoints (4, 8 and 12 weeks post-operatively). The patient's initial visit will include preoperative screening for eligibility, informed consent procedure, and recording of past medical history and physical exam. Once the patient is deemed eligible, enrolled, and signed informed consent, they will be randomized to either carbon dioxide AFL therapy or sham laser therapy. After the patient undergoes Mohs surgery with the resultant ulcer (the defect that typically forms after Mohs), the patient will undergo either carbon dioxide laser versus sham laser therapy. We will determine presence or absence of complete healing, wound temperature, a digital photograph, quality of life, and adverse events at each visit. Healing will be determined by one of the licensed research team members and will be defined by complete epithelialization in the absence of scab/eschar.

Wound temperature will be recorded by noninvasive infrared thermographic camera. A digital photograph will be taken with a camera that has an attachment ensuring the same distance and angle at every visit. Quality of life will be determined by ED-5Q questionnaire. Adverse events will be recorded by eliciting an oral history and review of the patient's diary. Adverse events will be recorded as presence of absence of specific outcomes. Outcomes that patients will be directly questioned about include: crusting (scaly or thickened scar), swelling, burning sensation, xerosis at treatment site, pruritus at treatment site, infection, bleeding, hypertrophic or keloid scarring, burns, or color changes at treatment site. These data points will be collected at every visit, and adjudicated by a member of the research team blinded to the treatment group. Placebo treatment will consist of directing the laser system at the floor instead of the patient's wound site. The patients will be wearing safety glasses and will have their wound site still anesthetized from the operation therefore unaware if they are receiving the therapy. This group will serve as the control group to the treatment arm in the study.

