Statistical / Data analysis: We estimate that 48 participants will be required to show a significant difference in time to 100% epithelialization between treatment and control during the 12 week study. A power analysis conducted in R(1) using the powerSurvEpi package(2) with alpha = 0.10 and beta = 0.20 suggested 24 participants per group or 48 total were required. We will employ various statistical techniques in addressing our study aims. For our first aim, efficacy: time to epithelialization will be modeled in a Cox regression as a function of covariates and treatment status. Temperature will be similarly modeled, but for these outcomes we will examine effects across time via a linear mixed model. For our second aim, safety: we intend to model incidence of infection as well as quality of life again across time using linear mixed models but this time based on non-inferiority comparisons. To address any attrition, we will employ per-protocol analysis. In the interest of safety, we plan to perform interim analyses at one month and discontinue the study if warranted.

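### The non-inferiority comparisons of infection and quality of life have no margin, alpha or deciding contrast, and the model named for infection is unreliable when infections are few

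*Combined protocol and SAP*

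**What the plan says.** The Statistical / Data analysis section states that, for safety, the team intends to "model incidence of infection as well as quality of life again across time using linear mixed models but this time based on non-inferiority comparisons". No margin, effect scale, confidence level or sidedness follows. Nor does the section say whether one visit or an average over visits decides the comparison.

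The only alpha appears earlier in that section and concerns efficacy. The plan says "48 participants will be required to show a significant difference in time to 100% epithelialization", and the power analysis "with alpha = 0.10 and beta = 0.20 suggested 24 participants per group". Sidedness is not given there either.

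Aim 1, under Objectives, lists "safety endpoints, including the incidence of wound infection" together with diary-based tolerability and quality of life. It ends by calling 48 a suitable sample size, without a calculation.

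Under Patient Visits and Data Collection, "Adverse events will be recorded as presence of absence of specific outcomes"; infection is one of the listed outcomes, and "These data points will be collected at every visit". For the other outcome, "Quality of life will be determined by ED-5Q questionnaire"; no score, standard deviation or margin is attached to it.

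On missing data the plan says only: "To address any attrition, we will employ per-protocol analysis". The per-protocol set is not defined.

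**The concern.** A non-inferiority test is defined by its margin and its error rate. Without them there is no null hypothesis to reject, and one set of results can be reported as non-inferior or not, depending on choices made later. Safety is one of only two aims, and non-inferiority is the only inferential rule the plan gives for it.

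Two features of the stated method add to this:

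- **Model.** A linear mixed model fitted to a present/absent outcome bases its bound on a normal approximation. With few infections the estimated variance is too small and the bound too optimistic, which favours a claim of safety.
- **Analysis set.** A per-protocol set can leave out patients who stop attending after an infection, who are the patients a safety comparison most needs.

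**Working it through.** **1. Where 48 comes from.** The plan's figure cannot be reproduced, because no hazard ratio or healing proportion is given. With the Schoenfeld formula, events = 4(z_α + z_β)²/(ln HR)², one can only solve for the hazard ratio that 48 implies. At two-sided 0.10 and 80% power, z_α + z_β = 1.645 + 0.842 = 2.486.

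- All 48 heal: HR = exp(2.486/√12) = 2.05.
- 70% heal (33.6 events): HR = exp(2.486/√8.4) = 2.36.
- If 0.10 is one-sided, these become 1.85 and 2.08.

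No safety quantity enters the calculation, so neither 48 nor its alpha carries over to infection or quality of life.

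**2. What the missing rule leaves open.** Assume 2/24 infections on laser and 1/24 on sham. The Newcombe upper bound is d + √[(u₁ − p₁)² + (p₂ − l₂)²], with p₁ = 0.0833, p₂ = 0.0417 and d = 0.0417. Here u₁ is the Wilson upper limit for 2/24 and l₂ the Wilson lower limit for 1/24.

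| One-sided alpha | u₁ | l₂ | Upper bound | 15-point margin | 20-point margin |
|---|---|---|---|---|---|
| 10% | 0.1849 | 0.0125 | 14.7 points | pass | pass |
| 5% | 0.2231 | 0.0094 | 18.5 points | fail | pass |
| 2.5% | 0.2585 | 0.0074 | 22.0 points | fail | fail |

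For the 5% row: 0.0417 + √(0.1398² + 0.0323²) = 0.185.

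**3. The linear model when infections are few.** The mixed model is approximated by the difference in subject means with pooled variance and a normal quantile, with the margin on the same scale as the mean. All outcomes with 24 per arm are enumerated under binomial probabilities. Assumptions: a 10-point margin, nominal one-sided 5%, and true rates exactly 10 points apart, so that every claim of non-inferiority is false.

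| True rates, laser v sham | Linear-model approximation | Newcombe |
|---|---|---|
| 12% v 2% | 10.5% | 3.1% |
| 15% v 5% | 8.7% | 5.0% |
| 20% v 10% | 6.3% | 5.6% |
| 30% v 20% | 5.6% | 5.7% |

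The case of no infection in either arm shows the mechanism. The pooled variance is zero, so the linear-model bound is 0 and passes any margin. The Newcombe bound at one-sided 5% is z²/(n + z²) = 2.706/26.706 = 10.1 points.

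**4. What 24 per arm gives.**

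- No infections in 24: upper limit 1 − 0.05^(1/24) = 11.7% (one-sided 95%).
- One infection per arm: Newcombe 95% interval ±16.4 points (Miettinen-Nurminen ±16.9).
- Quality of life at one visit: half-width t(0.975, 46 df) × √(2/24) = 2.013 × 0.2887 = 0.58 SD.
- Quality of life averaged over the visits at weeks 4, 8 and 12: multiply by √[(1 + 2ρ)/3]. This gives 0.42 SD at ρ = 0.3 and 0.52 SD at ρ = 0.7. The correlations are assumptions.

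**The case against.** **The alpha of 0.10 is trial-wide.** It is the only alpha in the plan, so this is a possible reading. The text, however, attaches it to the epithelialization power analysis. Even if it carried over, the margins and deciding contrasts would still be missing.

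**Safety does not depend on non-inferiority alone.** This stands. Diary-based tolerability, directly questioned adverse outcomes with blinded adjudication, adverse-event reporting and the one-month interim look need no margin. The gap concerns the two outcomes that the plan itself commits to non-inferiority.

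**Linear may be loose wording for a generalised model.** If so, step 3 falls away and the rest is unaffected. Newcombe is not uniquely right either: it slightly exceeds 5% in the last two rows of that table.

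**Aim 1 names incidence without saying per patient.** Correct. A reader might infer that the mixed model contradicts a stated per-patient endpoint. The documents state no such endpoint, and the statistical section models incidence across visits. Step 3 therefore puts margin and mean on one scale and does not rely on a mismatch.

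**One-visit quality-of-life precision is too pessimistic.** This also stands. The outcome is collected repeatedly and modelled over time, so the averaged figure is the fairer description, and adjustment for a baseline value could narrow it further.

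**Conclusion.** The concern holds. The two non-inferiority comparisons cannot be carried out as written without choosing margin, alpha and contrast later. The 2 v 1 example shows that this choice can reverse the conclusion.

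The model point is secondary and limited. Under the assumed rates and margin, the false-claim rate is about twice nominal at 12% v 2% and 8.7% at 15% v 5%, with almost no difference between methods from 20% v 10% upwards. The per-protocol point is a risk only, since the set is undefined.

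Two stronger readings are not supported:

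- **That 48 patients are too few for safety.** The Aim 1 statement has no stated safety basis, but adequacy depends on inputs the plan omits. With an assumed 5% infection rate in both arms and one-sided 5%, exact Newcombe power is 34%, 58% or 83% for margins of 10, 15 or 20 points.
- **That a claim of non-inferiority under a wide margin is necessarily an error.** If true rates were 15% v 5%, laser would be non-inferior under any margin above 10 points. The fault would lie in choosing that margin after seeing the data.

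**What to change.** - **Infection.** Define the endpoint as any wound infection by week 12, per patient, in all randomised patients. Report counts by arm and the risk difference with a Newcombe or Miettinen-Nurminen 95% confidence interval. Keep the per-protocol analysis as supporting, and report by arm how many patients lack week-12 data.
- **Quality of life.** Keep the linear mixed model, name one deciding contrast, and report the difference with a 95% confidence interval.
- **Non-inferiority.** Make no such claim for either outcome unless a margin and a one-sided alpha matching the interval (2.5% for a 95% interval) are fixed before unblinding. Otherwise, word Aim 1 as estimating safety.
- **Sample size sentence in Aim 1.** Replace it with the precision that 48 patients give: no infections in 24 is compatible with a rate up to about 12% (one-sided 95%); one infection per arm gives a 95% interval of about ±16 points; and the quality-of-life 95% interval is about ±0.42 to ±0.52 SD averaged over three visits, for an assumed correlation of 0.3 to 0.7.

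The cost is rewording of Aim 1 and the statistical section. The visits, data and patients stay the same. The downside is a more modest safety claim.

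### The plan does not say whether the surgery-day quality-of-life score is a pre-treatment baseline, or which visits the non-inferiority contrast covers

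*Combined protocol and SAP*

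**What the plan says.** Patient Visits and Data Collection sets the schedule: "We will determine presence or absence of complete healing, wound temperature, a digital photograph, quality of life, and adverse events at each visit". It counts the visits this way: "Patients will be seen at 4 separate visits to monitor safety and efficacy endpoints (4, 8 and 12 weeks post-operatively". Three of the four are named, so the fourth must be the surgery day. That gives one surgery-day score and three later ones.

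On the timing of the first score, the Purpose section reads: "Immediately after therapy and 4, 8, and 12 weeks postoperative patients will have a follow up visit". It has the survey filled in at those visits. Patient Visits and Data Collection describes an initial visit with a preoperative part (eligibility, consent, history and examination) but does not list the questionnaire there.

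On analysis, Statistical / Data analysis will model infection and "quality of life again across time using linear mixed models but this time based on non-inferiority comparisons". Covariates appear once, unlisted, for healing: "time to epithelialization will be modeled in a Cox regression as a function of covariates and treatment status". The next sentence reads: "Temperature will be similarly modeled, but for these outcomes we will examine effects across time via a linear mixed model". Whether the covariates carry over to temperature, and then to quality of life, is not stated.

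**The concern.** Quality of life is one of the Aim 1 tolerability measures and is to be judged by non-inferiority. Much of the spread in a generic health score usually lies between patients, and a score taken before treatment can remove part of it. With 24 per arm, a number chosen for healing time, precision on this endpoint is scarce.

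Two things are at stake. If the surgery-day score is not used as a baseline, the non-inferiority interval is wider than it need be. If it enters a single arm effect averaged over all visits, it contributes a difference that should be about zero, because treatment has had no time to act. That pulls the estimate toward no difference, which in a non-inferiority test favours the laser.

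**Working it through.** **Inputs from the documents.** The sample size calculation "suggested 24 participants per group or 48 total were required", run "with alpha = 0.10 and beta = 0.20". It concerns healing time only. It cannot be reproduced, because the hazard ratio and healing probabilities are not given, and it does not bear on quality of life. There is no stated figure for quality of life to reproduce.

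**Assumptions (none is in the documents).** SD 1 at each visit; equal correlation ρ between any two visits, 0.3 to 0.7; complete data; margin M = 0.5 SD; one-sided 5%. A decaying AR(1) correlation is the sensitivity check.

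**Step 1: variance of the arm contrast.** Each factor below is multiplied by 2/24.
- Mean of weeks 4, 8 and 12, no baseline: (1 + 2ρ)/3
- Same mean, baseline as covariate: (1 + 2ρ)/3 − ρ²
- Same mean as change from baseline: (1 + 2ρ)/3 + 1 − 2ρ

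| ρ | No baseline | Change score | Adjusted | Reduction v no baseline | Reduction v change |
|---|---|---|---|---|---|
| 0.3 | 0.533 | 0.933 | 0.443 | 17% | 52.5% |
| 0.5 | 0.667 | 0.667 | 0.417 | 37.5% | 37.5% |
| 0.6 | 0.733 | 0.533 | 0.373 | 49% | 30% |
| 0.7 | 0.800 | 0.400 | 0.310 | 61% | 22.5% |

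At ρ = 0.6 the SEs are √(0.733 × 2/24) = 0.247 with no baseline, √(0.533 × 2/24) = 0.211 for change and √(0.373 × 2/24) = 0.176 adjusted. The ratio 0.176/0.247 is 0.71, a 29% lower SE.

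A mixed model that keeps the surgery-day score as an outcome row but constrains the arms to a common baseline mean, solved by generalised least squares, gives the same factors as the covariate (0.417 at ρ = 0.5, 0.373 at 0.6).

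**Step 2: decaying correlation.** Under AR(1) at 0.6 the unadjusted factor is (3 + 4 × 0.6 + 2 × 0.36)/9 = 0.680. The covariance with baseline is (0.6 + 0.36 + 0.216)/3 = 0.392. The reduction is 0.392²/0.680 = 23%. At 0.5 and 0.7 it is 14% and 35%.

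**Step 3: power when the arms are truly equal,** Φ(M/SE − 1.645). At ρ = 0.6: Φ(0.5/0.247 − 1.645) = 65% without baseline and Φ(0.5/0.176 − 1.645) = 88% with it. At ρ = 0.5 it goes from 68% to 85%, and at 0.7 from 62% to 93%.

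**Step 4: one arm effect pooled over four visits.** A constant later difference d with zero on the surgery day averages (0 + d + d + d)/4 = 0.75d. The variance factor is (1 + 3ρ)/4. At a true loss equal to M, the chance of declaring non-inferiority is Φ(0.25M/SE − 1.645). At ρ = 0.6, SE = √(0.700 × 2/24) = 0.242, so Φ(0.125/0.242 − 1.645) = 13.0%. At ρ = 0.3, 0.4, 0.5 and 0.7 it is 15.5%, 14.4%, 13.6% and 12.4%. Under AR(1) at 0.4 to 0.8 the pooled effect retains 0.69 down to 0.58 of the difference.

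**Check.** In 20,000 simulated trials per setting at ρ = 0.5, 0.6 and 0.7, the adjusted to unadjusted variance ratio was 0.63, 0.52 and 0.39. False non-inferiority was 13.8%, 13.4% and 12.6% for the pooled effect, and 5.1% to 5.2% for the adjusted contrast.

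**The case against.** A reader might infer that the plan enters the surgery-day score as one more outcome row, with no baseline term. The documents do not say so. Modelling across time fits that reading, but it also fits a baseline covariate or a common-baseline model, and the covariates named for the Cox model may be meant to carry over. Nor is an outcome row the fault in itself: with a common baseline mean it loses nothing. The loss comes from having neither the adjustment nor the constraint.

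A reader might also infer that half the precision is lost. That holds for variance, not SE, near ρ = 0.6 with equal correlation and an unadjusted mean as comparator. Lower or decaying correlation gives much less.

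Third, a reader might infer that the comparison is biased toward non-inferiority. That needs one arm effect pooled over all four visits, which the plan does not name. Visit-specific contrasts have no dilution.

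The strongest objection is that the score may not be a baseline at all. The Purpose section places the first assessment after the laser or sham, so as written it may be post-treatment, and advice to adjust for it is premature until that is settled. This stands, and it sets the order of the fix. It is also fair that the missing non-inferiority margin is the larger gap, since no conclusion can be tested without one. Supplying a margin would not settle the role of the surgery-day score or the contrast, however.

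**Conclusion.** The point holds as under-specification. The plan states neither the role of the surgery-day score nor the arm contrast, and it does not secure the score as pre-treatment. Stating them offers a variance reduction of about 17% to 61% against no adjustment for equal correlation of 0.3 to 0.7, about 30% against a change score at 0.6, and 14% to 35% under AR(1) at 0.5 to 0.7.

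The rise in false non-inferiority from 5% to about 12% to 14% (correlation 0.4 to 0.7) is conditional on pooling all four visits, on a 0.5 SD margin and on a one-sided 5% level. It describes what the present wording leaves open, not what the plan has committed to. Every figure rests on an assumed correlation, and the power and error figures also rest on the assumed margin and level.

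**What to change.** 1. Reconcile the Purpose section with Patient Visits and Data Collection, and state that the surgery-day questionnaire is completed in the preoperative part of that visit.
2. State that this score is the baseline, used either as a covariate in the mixed model for the later scores or through a common baseline mean for the two arms.
3. Define the non-inferiority contrast on weeks 4, 8 and 12 only, saying whether it is their average or a named visit.

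The cost is about a sentence of analysis text and an earlier time for a form already due that day. It needs no extra visit or patient. The non-inferiority margin and its significance level must be supplied separately.

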Blinding: There will be one unblinded member of the team in this study which will be the clinician performing laser therapy or sham therapy, who will therefore not be involved in any data collection, but will be responsible for reporting any adverse events per IRB protocols at our institution. Other members of the research team member will be blinded to patient group assignment, and these members of the research team will collect data (see below) at subsequent visit. Additionally, patients will be blinded to treatment group. This will be achieved by having patients wear safety glasses which blind them and the wound site still anesthetized from the operation. Data collection will be done by a separate research team member who is blinded to the treatment groups.

Inclusion Criteria: Eligibility criteria will include patients older than 18 years, those with a lower extremity wound as a result of Mohs Micrographic Surgery at Saint Louis University Dermatology Des Peres, and a postoperative wound greater than 5mm in diameter. Patients must be able to understand the informed consent, willing to come to the office for treatments and capable of following post-treatment instructions.

Exclusion Criteria: Exclusion criteria will include pregnancy, breast feeding, immunosuppression, uncontrolled diabetes (defined as $>7\%$ A1c in the last 3 months), peripheral vascular disease, venous insufficiency, decompensated heart failure (NYHA class IV), peripheral neuropathy involving the treatment site, active cancer at the time of study enrollment excluding curatively treated skin cancer, and any underlying or current medical condition which, in the opinion of the Investigator, would interfere with the evaluation of the subject, or no desire/unable to undergo laser therapy. Immunosuppression will be defined as patients with HIV, AIDS, who have received an organ transplant, allogeneic bone marrow transplant, or peripheral stem cell transplant, and any other patients taking chronic doses of systemic immunosuppressive medication within 6 months prior to randomization. Examples of immunosuppressive medications include Tacrolimus, Azathioprine, Prednisone, or Methotrexate.

Patient Visits and Data Collection:

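### Attrition is handled only by an undefined per-protocol analysis; if patients who leave are dropped, the healing hazard ratio is biased whenever loss depends on healing and differs between arms

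*Combined protocol and SAP*

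**What the plan says.** The Statistical / Data analysis section of the combined protocol and SAP has one sentence on loss to follow-up: "To address any attrition, we will employ per-protocol analysis". It is not limited to any endpoint. No section says which patients form the per-protocol set, names an analysis of all randomised patients, or gives a censoring rule, an expected dropout rate or a sensitivity analysis.

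For efficacy, "time to epithelialization will be modeled in a Cox regression as a function of covariates and treatment status". Temperature, infection and quality of life go into linear mixed models, the last two as non-inferiority comparisons. Under Patient Visits and Data Collection, healing is judged only at clinic visits, with follow-up at weeks 4, 8 and 12. Treatment is one session (Purpose: "One group will receive a single laser treatment immediately after their surgery"). On blinding: "Additionally, patients will be blinded to treatment group".

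**The concern.** Because the sentence offers per-protocol analysis as the remedy for attrition, its natural reading is that a patient who stops attending is removed. Neither planned model needs this. A Cox model can use a patient up to the last attended visit, and a mixed model uses every observed visit.

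Removal is also an exclusion based on something that happens after randomisation. Healing is seen only at visits, so leaving and healing can be linked: a patient may give up on a slow wound, or stop coming once healed. If the link is present and the arms lose different numbers, the patients left are no longer comparable. Since the set is undefined, it could be settled after the data are seen, and no second analysis would show whether the exclusions changed the answer. For the non-inferiority comparisons a per-protocol result is useful beside an all-randomised one, but here it stands alone.

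**Working it through.** **1. The plan's own figure.** The plan gives alpha 0.10, beta 0.20 and 48 patients, but no HR, healing probability or sidedness. By the Schoenfeld formula, two-sided, events = 4(1.645 + 0.842)² / (ln HR)² = 24.73 / (ln HR)². If all 48 heal, ln HR = √(24.73/48) = 0.718 and HR = 2.05. If 24 heal, ln HR = √(24.73/24) = 1.015 and HR = 2.76. So 48 can be neither reproduced nor refuted, and nothing shows whether attrition was allowed for.

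**2. Inputs.** From the documents: 24 per arm, visits at weeks 4, 8 and 12, alpha 0.10. Assumed: two-sided test, 75% sham healing by week 12, Weibull shape 2, loss after weeks 4 and 8. 'Favourable' means significant for laser, nominally 5%.

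**3. Mechanism, in expected counts at true HR 1.0.** The cumulative hazard is −ln(0.25) × (t/12)² = 1.386 × (t/12)². The proportions unhealed at weeks 4, 8 and 12 are 0.857, 0.540 and 0.25. In each arm 24 × 0.143 = 3.43 patients (14.3%) heal by week 4.

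- *Unhealed laser patients leave, 15% per visit.* Lost: 24 × (0.15 × 0.857 + 0.85 × 0.15 × 0.540) = 4.74, leaving 19.26. All 3.43 early healers stay, so 3.43/19.26 = 17.8% appear healed by week 4, against 14.3% on sham. Laser looks better.
- *Already-healed laser patients skip later visits, 15% per visit.* Lost: 24 × [0.143 × (1 − 0.85²) + 0.317 × 0.15] = 2.09, leaving 21.91. Early healers kept: 3.43 × 0.7225 = 2.48, or 2.48/21.91 = 11.3%. Laser looks worse.

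**4. Simulated median HR** (Efron Cox on visit times, true HR 1.0; 3,000 to 10,000 trials per scenario).

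| Loss per visit | HR by exclusion | Favourable | HR by censoring |
|---|---|---|---|
| Laser only 15%, unhealed leave | 1.11 to 1.13 | about 9% | about 1.0 |
| Laser only 15%, healed skip visits | 0.90 | about 2% | about 1.0 |
| Sham only 15%, unhealed leave | about 0.90 | about 2% | about 1.0 |
| 10% laser v 5% sham, unhealed leave | about 1.04 | about 6% | about 1.0 |
| Unequal, unrelated to healing | no bias | – | about 1.0 |
| Equal 15%, unhealed leave | 1.00 | about 5% | about 1.0 |

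Varying sham healing over 50/75/90% and shape over 1/2/3 moves the first row only between 1.07 and 1.16. The loss pattern matters more, since it reverses the sign.

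**5. A second method.** A grouped-time proportional-hazards calculation with 50% sham healing and 30% laser v 10% sham loss gave, by exclusion, 1.11 when patients unhealed at week 4 left and 0.87 when healed patients skipped visits. All-randomised with censoring gave 1.00 in both.

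**6. Equal loss at true HR 2.3.** With complete follow-up the median HR is about 2.2 and power 81%. Equal 15% loss of unhealed patients lowers the exclusion HR to 2.13. Equal 15% loss of healed patients raises it to about 2.25. Power with equal 15% loss is 71% by exclusion and 74% by censoring if unhealed patients leave, and 67% against 74% if loss ignores healing. Exclusion therefore costs about 3 to 7 points beyond censoring.

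**7. Where censoring fails.** Take laser-only loss of 30% per visit among patients who will not heal by week 12, otherwise 7.5%, at true HR 1.0: exclusion gives 1.31 and censoring 1.18. If the 30% applies instead to patients about to heal by the next visit, exclusion gives 0.98 and censoring 0.85.

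**The case against.** The sentence does not say in words that leavers are excluded. Treatment is one session on the day of surgery, so a set defined by treatment received could keep every treated patient. That stands as a possible reading, but it needs a definition the plan does not give.

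Patients and assessors are blinded, which makes strongly differential loss less likely, and no dropout rate in the documents supports the one-arm scenarios. This also stands. In the milder case the shift is only to about 1.04, and with equal loss, or loss unrelated to healing, there is no bias at HR 1.0. Blinding lowers the chance of differential loss without excluding it.

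Censoring is not uniformly better: step 7 has a case where it does worse than exclusion. That is a reason to add analyses of assumed outcomes, not to keep an undefined exclusion rule.

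Three stronger readings are tempting and are not supported. A reader might infer that the plan tilts the result towards laser; the direction depends on which arm loses patients and whether they are slow or fast healers, and the documents say neither. A reader might infer that equal loss always attenuates a real effect; it can move the HR slightly either way. A reader might infer that the 80% power assumes all 48 are followed to week 12; the plan gives only alpha, beta and the sample size.

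**Conclusion.** The concern holds in a conditional form. The only stated attrition rule is undefined, has no all-randomised analysis beside it and, on its natural reading, discards usable data. If loss is related to healing and differs between arms, exclusion moves a true HR of 1.0 to about 1.11 to 1.13 or to about 0.90 under 15% one-arm loss, and to about 1.04 under 10% against 5%. At HR 2.3 with equal 15% loss it costs about 3 to 7 points of power beyond censoring. These figures rest on 75% sham healing, Weibull shape 2, a two-sided test and assumed loss patterns; none comes from the documents, so they illustrate what could happen and do not show bias in this trial. The case for change rests on the missing definition and missing comparison analysis, which can be read directly from the plan.

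**What to change.** Replace the sentence with:

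> The primary analysis includes all randomised patients in the arm assigned. Patients whose healing was recorded count as events at that visit even if they miss later visits; patients who leave before healing is recorded are censored at their last attended visit. Mixed models use all available visits. A per-protocol set, defined before unblinding, is a sensitivity analysis, shown beside the all-randomised result for the non-inferiority comparisons.

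Report loss by arm, visit and healing status. Add a sensitivity analysis that varies the assumed outcome of lost patients separately in each arm, from healed at the next scheduled visit to unhealed through week 12. Neither end is conservative in general: at true HR 1.0 with 15% one-arm loss of unhealed patients, assuming no healing through week 12 gives about 0.75 if laser loses patients and 1.32 if sham does. State whether the 80% power allows for attrition.

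The cost is one SAP paragraph, one definition and one set of sensitivity analyses, with no extra patients or data. Power lost to attrition itself is not recovered, and censoring adds nothing for a patient who never returns after surgery.

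Separately, reconcile the order of randomisation and surgery. Purpose says "After surgery patients will be randomized into two groups". Patient Visits and Data Collection says "Once the patient is deemed eligible, enrolled, and signed informed consent, they will be randomized" and only then describes the operation ("After the patient undergoes Mohs surgery with the resultant ulcer"). Study Design places randomisation on the surgery day, after eligibility is determined. Since entry requires "a postoperative wound greater than 5mm in diameter", the order decides whether a randomised patient can later prove ineligible.
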